4.2.2 Justification for Dose

The planned dose of pembrolizumab for this study is 200 mg every 3 weeks (Q3W). Based on the totality of data generated in the Keytruda development program, 200 mg Q3W is the appropriate dose of pembrolizumab for adults across all indications and regardless of tumor type. As outlined below, this dose is justified by:

- Clinical data from 8 randomized studies demonstrating flat dose- and exposure-efficacy relationships from 2 mg/kg Q3W to 10 mg/kg every 2 weeks (Q2W),
- Clinical data showing meaningful improvement in benefit-risk including overall survival at 200 mg Q3W across multiple indications, and
- Pharmacology data showing full target saturation in both systemic circulation (inferred from pharmacokinetic [PK] data) and tumor (inferred from physiologically-based PK [PBPK] analysis) at 200 mg Q3W

Among the 8 randomized dose-comparison studies, a total of 2262 participants were enrolled with melanoma and non-small cell lung cancer (NSCLC), covering different disease settings (treatment naïve, previously treated, PD-L1 enriched, and all-comers) and different treatment settings (monotherapy and in combination with chemotherapy). Five studies compared 2 mg/kg Q3W versus 10 mg/kg Q2W (KN001 Cohort B2, KN001 Cohort D, KN002, KN010, and KN021), and 3 studies compared 10 mg/kg Q3W versus 10 mg/kg Q2W (KN001 Cohort B3, KN001 Cohort F2 and KN006).

All of these studies demonstrated flat dose- and exposure-response relationships across the doses studied representing an approximate 5- to 7.5-fold difference in exposure. The 2 mg/kg (or 200 mg fixed-dose) Q3W provided similar responses to the highest doses studied. Subsequently, flat dose-exposure-response relationships were also observed in other tumor types including head and neck cancer, bladder cancer, gastric cancer and classical Hodgkin Lymphoma, confirming 200 mg Q3W as the appropriate dose independent of the tumor type. These findings are consistent with the mechanism of action of pembrolizumab, which acts by interaction with immune cells, and not via direct binding to cancer cells.

Additionally, pharmacology data clearly show target saturation at 200 mg Q3W. First, PK data in KN001 evaluating target-mediated drug disposition (TMDD) conclusively demonstrated saturation of PD-1 in systemic circulation at doses much lower than 200 mg Q3W. Second, a PBPK analysis was conducted to predict tumor PD-1 saturation over a wide range of tumor penetration and PD-1 expression. This evaluation concluded that pembrolizumab at 200 mg Q3W achieves full PD-1 saturation in both blood and tumor.

Finally, population PK analysis of pembrolizumab, which characterized the influence of body weight and other participant covariates on exposure, has shown that the fixed-dosing provides similar control of PK variability as weight based dosing, with considerable overlap in the distribution of exposures from the 200 mg Q3W fixed dose and 2 mg/kg Q3W dose. Supported by these PK characteristics, and given that fixed-dose has advantages of reduced dosing complexity and reduced potential of dosing errors, the 200 mg Q3W fixed-dose was selected for evaluation across all pembrolizumab protocols.

The FDA approved dose for treatment of BRCA positive ovarian and breast cancers [Pujade-Lauraine et al., 2017; Ledermann et al., 2012] of olaparib 300mg orally (PO) twice daily (BID) will be utilized.

The dose of olaparib used in this study is 300 mg twice daily which is the currently approved dose.

One cycle is defined as 3 weeks or 21 days, and both drugs (pembrolizumab and olaparib) will be started on day 1 of cycle 1. Overlapping toxicities to the combination are not expected. However, the first six patients on the study will be evaluated for any grade 4 hematologic or grade 3 or higher non-hematologic toxicity during the first two cycles of treatment. Adjustment of the doses of olaparib to 300 mg PO daily will be made in subsequent patients if grade 4 hematologic toxicities lasting longer than 7 days, neutropenic fevers or grade 3 non-hematologic toxicities lasting longer than 7 days are observed in at least three of the initial six patients. If intolerable toxicities arise after three or more cycles in patients otherwise experiencing clinical benefit, patients will have the option to continue pembrolizumab as monotherapy. Special attention will be placed on persistent grade 3 or higher anemia, as myelodysplastic syndromes have been described in around 1.5% of patients receiving olaparib in previous trials [Pujade-Lauraine, et al., 2017; Ledermann et al., 2012; Moore et al., 2014].

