1.0 TRIAL SUMMARY

Abbreviated Title	Pembrolizumab and Olaparib in Cervical Cancer Patients
Trial Phase	II
Clinical Indication	Cervical Cancer
Trial Type	Therapeutic
Type of control	None
Route of administration	Intravenous and Oral
Trial Blinding	None
Treatment Groups	One
Number of trial participants	48
Estimated enrollment period	2-3 years
Estimated duration of trial	3-4 years
Duration of Participation	Until lack of clinical benefit is demonstrated.
Estimated average length of treatment per patient	6 months

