2.0 TRIAL DESIGN

The study is a non-randomized, open-label phase II clinical trial of the PD-1 inhibitor pembrolizumab, in combination with the PARP inhibitor olaparib, in patients with stage IV, unresectable or recurrent cervical cancer after failure of first-line therapy.

Patients will be treated with standard doses of pembrolizumab, 200 mg intravenously (IV) every 3 weeks [Chung et al., 2019], which is approved for metastatic cervical cancer patients with PDL-1 expression (CPS ≥ 1) and disease progression on or after chemotherapy. They will also receive olaparib 300mg orally (PO) twice daily (BID), which is the FDA approved dose for treatment of BRCA positive ovarian and breast cancers [Barber et al., 2013; Swisher, 2008; Bouwman et al., 2010; Robson et al., 2017]. One cycle is defined as 3 weeks or 21 days, and both drugs will be started on day 1 of cycle 1. Treatment will be continued until progressive disease or unacceptable toxicity. Evaluation for response with imaging (CT or MRI) will be performed every 9 weeks (3 cycles) using Immune Response Evaluation Criteria (iRECIST) [Seymour et al., 2017]. By this set of criteria, progression will need confirmation with a repeat scan at least four weeks later to rule out the rare but occasionally seen pseudo-progression. New lesions are added to the total burden of disease and only by themselves do not represent progression.

Treatment beyond initial investigator-assessed iRECIST-defined progression will be permitted in a case-by-case basis if the treating physician can document that the patient is experiencing clinical benefit and is tolerating study therapy.

Overlapping toxicities to the combination are not expected. However, the first six patients on the study will be evaluated for any grade 4 hematologic or grade 3 or higher non-hematologic toxicity during the first two cycles of treatment. Adjustment of the doses of olaparib to 300 mg PO daily will be made in subsequent patients if grade 4 hematologic toxicities lasting longer than 7 days, neutropenic fevers or grade 3 non-hematologic toxicities lasting longer than 7 days are observed in at least three of the initial

[figure not shown]

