5.8 Participant Replacement Strategy

We anticipate enrollment of 48 patients for which tumor and toxicity assessments following pembrolizumab/olaparib administration can be made. We will replace patients enrolled for which clinical trial discontinuation was performed prior to any administration of pembrolizumab or those for which pembrolizumab is discontinued due to acute hypersensitivity reactions during the first administration of pembrolizumab. An attempt will be made to assess tumor response in all enrolled patients as specified in the protocol. Patients experiencing clinical deterioration after two doses of pembrolizumab, will be considered treatment failures, will count as tumor progression, and will not be replaced.

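### The first-six toxicity rule has a fixed denominator and no definition of an evaluable patient, so early leavers without toxicity lower its chance of triggering

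*Combined protocol and SAP*

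**What the plan says.** Sections 2.0 and 4.2.2 state the same rule. In 2.0, "the first six patients on the study will be evaluated for any grade 4 hematologic or grade 3 or higher non-hematologic toxicity". Section 4.2.2 limits this to "toxicity during the first two cycles of treatment" and states that "One cycle is defined as 3 weeks or 21 days", which makes the window 42 days. The olaparib dose for subsequent patients changes if events on a listed set of criteria "are observed in at least three of the initial six patients". Those criteria are grade 4 hematologic toxicity beyond 7 days, neutropenic fever, and grade 3 non-hematologic toxicity beyond 7 days.

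Section 5.8 gives two grounds for replacement. The first is "We will replace patients enrolled for which clinical trial discontinuation was performed prior to any administration of pembrolizumab". The second is that "pembrolizumab is discontinued due to acute hypersensitivity reactions during the first administration of pembrolizumab". Patients who deteriorate clinically after two doses count as progressions and are not replaced. The section opens by speaking of 48 patients in whom tumor and toxicity can be assessed, and 4.2.1 calls the 48 evaluable. Neither statement is tied to the first six or to two cycles.

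Section 6.2.1 has AEs reported for 30 days after study treatment ends, and serious AEs for up to 90 days. The schedule in 2.3, as extracted from the PDF, shows blood counts at screening and at treatment cycles, with none at discontinuation or later.

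**The concern.** The rule's window is two cycles on treatment, but its denominator is whoever enrolled first. Suppose one of the six stops in week 3 for clinical deterioration, withdrawal or death from disease. She has not shown whether two cycles of the combination are tolerable. Neither replacement ground in 5.8 covers her. Dose two falls at about day 22, so the group that 5.8 says is not replaced can also fall inside the 42-day window.

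Applied literally, she remains one of the six and adds to the count only if a qualifying event was observed. The threshold then becomes, in effect, three of five informative patients, or three of four if two leave. The error runs in one direction: the rule becomes less likely to fire when the regimen is poorly tolerated. It is the only numeric cohort-level toxicity trigger in the plan, and it determines the olaparib dose for up to 48 − 6 = 42 later patients. If the point is left open, how to read a partly observed six will be decided after the data are seen.

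**Working it through.** **The plan's own figures.** No operating characteristics are given for the first-six rule. The only design calculation is for efficacy in 7.2 (48 patients, success at 10 or more responses, 0.13 against 0.28). Exact binomial tails give error rates of 0.0865 and 0.0995, against the stated 0.087 and 0.099. That design reproduces and is not affected by this point.

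**Inputs from the documents.** Six patients; threshold of three; window 2 × 21 = 42 days; the two replacement grounds in 5.8.

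**Inputs assumed.** The documents give neither the true rate of qualifying toxicity, p, nor the chance q that a patient leaves early for a reason unrelated to toxicity. Both are varied below. A leaver is given a fraction f of the full toxicity risk: f = 0 if she is uninformative, f = 0.5 if she carries half the risk.

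**Step 1: fixed number of uninformative leavers.** With k leavers, P(trigger) = P(X ≥ 3) for X ~ Binomial(6 − k, p). At p = 0.5:
- k = 0: (20 + 15 + 6 + 1)/64 = 42/64 = 0.656
- k = 1: (10 + 5 + 1)/32 = 16/32 = 0.500
- k = 2: (4 + 1)/16 = 5/16 = 0.313

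| Assumed p | Six observed | One leaver | Two leavers |
|---|---|---|---|
| 0.20 | 0.099 | 0.058 | 0.027 |
| 0.33 | 0.313 | 0.205 | 0.108 |
| 0.40 | 0.456 | 0.317 | 0.179 |
| 0.50 | 0.656 | 0.500 | 0.313 |
| 0.60 | 0.821 | 0.683 | 0.475 |

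**Step 2: one leaver at half risk.** P = P(X5 ≥ 3) + P(X5 = 2) × 0.5p, where X5 counts events among the other five patients. At p = 0.5 this is 0.500 + (10/32) × 0.25 = 0.578. At p = 0.33, 0.40 and 0.60 it is 0.259, 0.387 and 0.752.

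**Step 3: averaged over the number of leavers.** If each patient leaves early with probability q, independently of toxicity, the per-patient event probability is p(1 − q) + q·f·p, and the trigger probability is the Binomial(6) tail at that value. At p = 0.5:
- q = 0.05, f = 0: rate 0.475, P = 0.6083
- q = 0.20, f = 0: rate 0.400, P = 0.4557
- q = 0.05, f = 0.5: rate 0.4875, P = 0.6325
- q = 0.20, f = 0.5: rate 0.450, P = 0.5585

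All four compare with 0.6562 when nobody leaves.

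**Step 4: how often this arises.** P(at least one leaver in six) = 1 − (1 − q)^6. This is 1 − 0.95^6 = 0.26 at q = 0.05 and 1 − 0.80^6 = 0.74 at q = 0.20. P(two or more) is 0.03 and 0.34.

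**The case against.** The strongest reply is that the protocol never says an early leaver is scored as free of toxicity. A reader might infer such a scoring rule, but the text does not contain one. What is there is a fixed six, a count of observed events and no evaluability definition; the scoring follows only if these are applied literally. That part of the reply stands.

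It is also fair that leavers are not lost from view. With AE reporting for 30 days after cessation, a patient who stops on day 14 is followed to day 44, past the end of the window. This narrows the gap, and it is why the half-risk figures are shown. It does not close the gap. Her exposure is shorter than the two cycles being judged, and two of the three criteria need an event lasting more than 7 days, which death or withdrawal can cut off. The schedule as extracted also shows no blood count after treatment cycles, so a hematologic event could go unmeasured.

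Two further inferences should be resisted. From the 6-month figure for "Estimated average length of treatment per patient" in 1.0, a reader might take an exponential and get 1 − exp(−(42/30.44)/6) = 20.5% off treatment by day 42, hence 1 − 0.795^6 = 75% for at least one of six. The 6-month average covers exits for every reason, including toxicity. A constant hazard this early is doubtful too: entry requires ECOG 0 to 1 and life expectancy of at least 16 weeks, and the first scheduled scan is at week 9. The documents therefore do not support that rate for non-toxic exits.

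A reader might also conclude that nothing else protects patients. That is not so. Section 5.9 allows termination for the incidence or severity of adverse reactions, and 5.2.2 and 6.2.1.1 to 6.2.1.3 set dose rules for individual patients. No passage pauses enrollment after six patients, so 42 is the most that could be treated on the reading. The rule changes a dose; it does not stop the trial.

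**Conclusion.** The concern holds as a gap in the rule's definition that has a material effect when the text is applied literally. At an assumed true rate of 50%, one uninformative leaver lowers the trigger probability by about 16 points (0.656 to 0.500), or about 8 points if she carries half the risk (to 0.578). Two uninformative leavers lower it by about 34 points (to 0.313). Averaged over an assumed 5% to 20% early exit, the loss is about 5 to 20 points with zero-risk leavers and about 2 to 10 points with half-risk leavers.

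The direction is the same at every assumed rate; the size rests on p, q and f, none of which the documents supply. The same mechanism lowers triggering at low rates (0.099 to 0.058 at 20% with one leaver), so scoring on evaluable patients restores the rule's full-six behavior at both ends. The efficacy design is untouched.

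**What to change.** In 2.0 and 4.2.2, score the rule on the first six toxicity-evaluable patients: those who have a qualifying toxicity, or who complete the two-cycle window. The sponsor should define completion, in particular whether it means exposure or follow-up.

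For this rule only, a patient who leaves earlier for a reason unrelated to toxicity is replaced by the next enrolled patient. A patient who leaves because of any toxicity, including one that misses the listed criteria, is not replaced out of the six, and the sponsor states how she is counted. Add a sentence to 5.8 so that its replacement grounds and this one do not conflict.

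Every patient stays in the 48 for the efficacy and safety analyses. The toxicity criteria, the three-of-six threshold and the dose consequence are left to the sponsor.

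The cost is a wording change. The downside is that the reading of the rule may wait for one or two more patients who are being enrolled anyway.

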4.2.3 Rationale for Endpoints

4.2.3.1 Efficacy Endpoints

The primary clinical endpoint is overall Objective Response Rate by iRECIST criteria (iORR).

Secondary clinical endpoints will include Progression Free Survival (PFS) and Overall Survival (OS) and safety and tolerability per the Common Terminology Criteria for Adverse Events (CTCAEv5.0) (Common Terminology Criteria for Adverse Events https://ctep.cancer.gov/protocoldevelopment/electronic_applications/docs/CTCAE_v5_Quick_Reference_8.5x11.pdf. Accessed September 30, 2018).

Although cervical cancer is curable in early stages, once it has recurred or metastasized less than 20% of patients survive 5 years (Howlader et al., 2017). Pembrolizumab was recently approved for treatment of PD-L1 positive cervical cancer patients in the second line metastatic setting, with an ORR of only 12.2% in the general population on study (Chung et al., 2019). A proposed model to increase pembrolizumab activity is through increasing tumor mutational load and formation of neoantigens expressed on cancer cells, thereby leading to greater recognition of those tumor cells by the immune system (Rizvi et al., 2015; Snyder et al., 2014; Van Allen et al., 2015). This strategy could be achieved through either enriching treated populations with cancer patients harboring innate (germline or somatic) DNA repair deficiencies, by combining immune checkpoint inhibitors with compounds causing DNA damage, such as platinum and other alkylating agents, or using compounds that directly inhibit DNA repair, such as (PARP) inhibitors.

Olaparib is an oral inhibitor of PARP, causing synthetic lethality in BRCA1/2 deficient tumors and is FDA approved for the treatment of metastatic breast and ovarian cancers harboring germline mutations in the BRCA genes or as maintenance in ovarian cancer patients with tumors experiencing prior sensitivity to platinum agents [Pujade-Lauraine et al., 2017; Robson et al., 2017; Ledermann, et al., 2012].

We expect that the combination of pembrolizumab and olaparib in patients with advanced cervical cancer after failure of chemotherapy will lead to increased efficacy compared to single agents in this population, and that the increase in efficacy will be substantial in those patients harboring homologous recombination repair and other deficiencies in DNA damage repair. We also expect that the combination will be safe and tolerable without significant overlapping toxicities.

4.2.3.2 Planned Exploratory Biomarker Research

One of the barriers to the generalized applicability of immunotherapy is the identification of patients who will derive the most benefit from this type of therapy, and better predictive biomarkers are urgently needed.

Correlative endpoints in this study will include determining the functional status of the Fanconi Anemia pathway in promoting homologous recombination repair as well as describing the microbiome composition in responsive and non-responsive patients.

Fanconi Anemia pathway analysis

The principal correlative endpoint is to evaluate if baseline tumor deficiencies in the FA pathway are associated with antitumor responses to the combination of pembrolizumab and olaparib, as assessed by the FATS1 assay performed on archived paraffin embedded tumor tissues.

Since somatic mutations have the potential to encode "non-self" immunogenic antigens, tumors with a large number of somatic mutations due to mismatch-repair defects are predicted to be susceptible to immune checkpoint blockade. Following this logic, tumors with other types of repair deficiency, such as homologous recombination repair would plausibly have a large number of somatic mutations and would likely be susceptible to immune checkpoint blockade.

The FATS1 assay has the ability to differentiate between functionally deficient and functionally competent Fanconi Anemia pathway tumors and therefore, could be used to identify additional patients susceptible to pembrolizumab. We hypothesize that the efficacy of immune checkpoint inhibitors could be increased by combining them with compounds causing DNA damage, or compounds causing inhibition of DNA repair such as (PARP) inhibitors. Thus targeting both HR repair and immune checkpoints will result in a synergistic anti-tumor effect. We expect that patients with pre-existing homologous recombination repair as assessed by FATS1 would benefit the most from this combination approach.

The FATS1 assay will be performed to assess functional deficiency of the FA pathway, as previously described [Duan et al., 2013; Villalona-Calero et al., 2016] using archived paraffin embedded tumors. We hypothesize that a FATS1 negative result, correlated with a higher mutational burden, will be associated with a better response rate. FA deficiency in tumors is not required for enrollment on the trial, thus patients with both FA functionally deficient tumors and patients with FA functionally competent tumors will be receiving treatment. Based on prior screening data in solid tumors [Villalona-Calero et al., 2016], we anticipate that approximatively 30% of patients in this trial will be FA functionally deficient.

FFPE tumor tissue will be cut at 4 microns, placed on positively charged slides and stained with hematoxylin and eosin. Additional sections for immunofluorescence staining will be placed in a 60oC oven for 1 h, cooled, deparaffinized and rehydrated through xylenes and graded ethanol solutions to water in standard fashion. Antigen retrieval will be performed by placing slides in Dako's TRS (pH 6.1) antigen retrieval solution (Dako, Carpenteria, CA) in a calibrated vegetable steamer (Black & Decker). Slides will then be placed on a Dako Autostainer for automated staining. Subsequently, tissue sections will be incubated for 1 hour at room temperature with a primary antibody cocktail of rabbit polyclonal FANC-D2 antibody at a dilution of 1:1000 and a monoclonal anti-Ki67 mouse antibody at a dilution of 1:150. Sections will then be co-incubated for 1 hour at room temperature with a secondary antibody (FITC conjugated to anti-rabbit IgG and Alexafluor 594 donkey anti-mouse) at 1:1000. All rinses will be performed on the autostainer with TBST. The sections will be mounted on glass slides using a 4' 6-diamidino-2-phenylindole (DAPI)-containing embedding medium (Vysis Dapi 1, Abbott Laboratories, Downers Grove, IL). FANCD2 foci positive and negative cell lines (MCF-7 and PD20 cells) will be used as controls. Slides will be analyzed under a Nikon E-400 fluorescence microscope. Ki-67 nuclear positivity of greater than 10% (Ki-67/DAPI) is required to consider a sample evaluable. Evaluation of a total of 300 cells (300 DAPI stained nuclei) with less than one foci positive nucleus per 100 cells is the benchmark to define FA pathway deficiency through FATS1.

Exploratory Correlative Endpoints include determining if increased baseline tumor mutation burden (TMB), MSI, and PD-L1 expression correlate with FATS1 negativity, and if these findings are independently associated with response to therapy.

